- Difference in HM-PRO total and domain scores between allo-SCT and CAR-T groups at each time point (T1–T5)

Secondary Endpoints:

- Change in HM-PRO scores over time within each group
- Comparison of PROs by disease status and treatment line
- Frequency and severity of adverse events and correlation with PRO data

8. Statistical Analysis

- All analyses will be performed using two-sided tests with a nominal significance level of $\alpha = 0.05$ unless otherwise stated. Estimates will be reported with 95% confidence intervals.

Primary analysis population include all enrolled participants with at least one post-baseline HM-PRO assessment (intention-to-observe principle).

- Baseline demographic and clinical variables will be summarized by treatment group (allo-SCT vs CAR-T).

- **Continuous variables:** mean (SD) and median (IQR) as appropriate.
- **Categorical variables:** counts and percentages.
- Between-group baseline comparisons will be descriptive (t-tests/Wilcoxon tests or chi-square/Fisher exact tests) to display balance; inferential testing of baseline covariates is not the primary focus. A baseline table will be produced.

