8.1 Primary longitudinal analysis (HM-PRO)

- **Primary modelling approach:** linear mixed-effects models (LMM) for repeated measures of HM-PRO scores to evaluate within-hospital trajectories and between-group differences. The base model will include:
 - Fixed effects for **timepoint (categorical: T1, T2, T3, T4, T5), treatment group**, and the **group × time** interaction (to test for differential trajectories).
 - A random intercept for participant to account for within-subject correlation; random slope for time will be considered if supported by data and model fit.
 - Prespecified covariates: baseline HM-PRO score (if modelling discharge score via ANCOVA alternatively), age, sex, disease type, disease status, line of therapy, major comorbidity index, and site (as fixed effect or as random effect in a hierarchical model).

- Parameter of interest: the group \times time interaction contrasts (e.g., difference in mean change from baseline to discharge between groups). Report estimated marginal means (least-squares means), differences, 95% CIs and p-values.
- **Model diagnostics:** check residuals for normality and heteroscedasticity, influence diagnostics, and perform sensitivity analyses using robust standard errors if necessary. If severe non-normality persists, consider transformation or a generalized linear mixed model (GLMM) or rank-based mixed model.

Repeated measures ANOVA

- As a supportive analysis (or when assumptions are met and complete data are available), repeated-measures ANOVA (with Greenhouse-Geisser correction if sphericity violated) may be used to summarize overall time and group effects. Primary inference will rely on mixed models which better accommodate missingness and unequal intervals.

Between-group comparisons & ANCOVA

- For the primary endpoint specified as change from baseline to discharge, an **ANCOVA** model will be used (discharge HM-PRO as outcome, baseline HM-PRO as covariate, plus the same prespecified covariates). This produces an adjusted estimate of the between-group difference in mean change.
- Unadjusted two-sample t-tests (or nonparametric Wilcoxon tests) will be presented for transparency.

Subgroup analyses

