- Exploratory subgroup analyses will be performed for: disease type (AML vs lymphoma vs myeloma), disease status (remission vs progression), age strata, and treatment line. Each subgroup analysis will include a formal **interaction test** (group \times subgroup) within the primary model rather than separate stratified unadjusted tests. Subgroup results are exploratory and interpreted cautiously.

Correlation / association between adverse events and PROs

- **Correlation analyses:** relationship between AE burden (grade or counts) and HM-PRO scores will be examined using Spearman's rank correlation (for ordinal AE grades) or Pearson correlation if assumptions hold.
- **Regression analyses:** to examine whether specific AEs (e.g., CRS, ICANS, mucositis, infections, GvHD) are associated with concurrent or subsequent HM-PRO scores, include AE indicators or graded severity as fixed effects in the mixed model (time-varying covariates). Logistic or Poisson regression (or negative binomial) may be used where appropriate (e.g., modelling probability of clinically meaningful deterioration, or AE counts). Report adjusted effect estimates (e.g., mean differences, odds ratios, incidence rate ratios) with 95% CIs.

- Pre-specify temporal directionality in the SAP (e.g., whether AEs occurring before an HM-PRO assessment are considered predictors).

Handling of missing data

- **Item-level HM-PRO missingness:** per the HM-PRO scoring manual, **missing item responses will not be substituted**; scores will be calculated according to the instrument's guidance.
- **Missing assessments / visit-level missingness:** for missing entire HM-PRO assessments (e.g., missed T2, T3, T4 or T5), the primary approach will be **multiple imputation by chained equations (MICE)** under a missing at random (MAR) assumption. Imputation models will include baseline and post-baseline HM-PRO items/scores, demographic and clinical covariates, laboratory markers, site, and indicators predictive of missingness. We will perform at least $m = 20$ imputations (or more if fraction of missing information is high) and combine estimates by Rubin's rules.
- **Sensitivity analyses:** compare results from: complete-case analysis, multiple imputation, and worst-case / tipping-point analyses to assess robustness to missing not at random (MNAR) mechanisms. The SAP will detail variables included in imputation models and diagnostics for imputation quality.

Multiplicity and inference

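### The planned group × subgroup test in the five-visit mixed model cannot show whether the group difference in change from admission to discharge varies by subgroup

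*Protocol*

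**What the plan says.** All of this is in the Protocol, mainly Section 8.1.

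- **Primary model.** The primary approach is "linear mixed-effects models (LMM) for repeated measures of HM-PRO scores to evaluate within-hospital trajectories and between-group differences". Its fixed effects are "timepoint (categorical: T1, T2, T3, T4, T5), treatment group" and the group × time interaction, with a random intercept per participant and a random slope only if the data support it. Admission (T1) is therefore one of the outcome levels.
- **Parameter of interest.** It is the set of group × time contrasts, for example the "difference in mean change from baseline to discharge between groups". Section 3.1 gives the matching estimand: the mean difference in change score between CAR-T and allo-SCT.
- **Which analysis carries inference.** "Primary inference will rely on mixed models which better accommodate missingness and unequal intervals".
- **Subgroup test.** The factors are "disease type (AML vs lymphoma vs myeloma), disease status (remission vs progression), age strata, and treatment line". Each gets a formal interaction test, written as group × subgroup and placed "within the primary model rather than separate stratified unadjusted tests". No time factor appears in that term. The paragraph ends: "Subgroup results are exploratory and interpreted cautiously".
- **ANCOVA.** Section 8.1 also gives an ANCOVA of the discharge score on the baseline score and covariates, for the endpoint defined as change from baseline to discharge.

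**The concern.** The plan's question is about change: does the shift in HM-PRO from admission to discharge differ between CAR-T and allo-SCT? A subgroup analysis that follows from it asks whether that difference in change varies by disease type, disease status, age or treatment line. In a model where time is a factor and T1 is an outcome, that needs a term that varies with both visit and subgroup. The stated term varies with subgroup only.

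Two misreadings could follow. Treatment is allocated by clinical indication, so the groups may already differ at admission, and by different amounts in, say, patients in remission and in progression. The planned test would register such a gap although nothing about the hospital course differs. Conversely, a real difference between subgroups in the course could go undetected, depending on when in the stay it appears.

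**Working it through.** **1. The plan's own figures.** Section 8.2 gives no figure for the subgroup test. Its sample sizes reproduce to within one patient with n = 2(1.960 + 0.842)²σ²/6²:

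- SD 12: 62.8, so 63.
- SD 15: 98.1 (stated as 98; rounding up gives 99).
- SD 15 with r = 0.5: 98.1 × 0.75 = 73.6, so 74.
- 73.6 × 1.1 = 80.9, so 81.

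**2. Cancellation.** Write the mean at visit t, group g (0/1) and subgroup s (0/1) as

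μ(t,g,s) = τ_t + g·γ_t + s·δ + g·s·θ,

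where γ_t carries group and group × time, and θ is the group × subgroup term. The group difference in change in subgroup s is

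[μ(5,1,s) − μ(1,1,s)] − [μ(5,0,s) − μ(1,0,s)] = γ_5 − γ_1.

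Both δ and θ drop out, so the expression is the same for s = 0 and s = 1. This is algebra on the fixed effects and holds with or without random slopes.

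**3. What θ estimates.** With a random intercept and complete visits, the generalised least squares estimator of θ puts weight 0.2 on each of T1 to T5 (checked at correlations 0.3, 0.5 and 0.7). It is the plain five-visit average, with T1 supplying 20%. Under one illustrative random-slope structure the weights are 0.378, 0.289, 0.200, 0.111 and 0.022, so T1 then weighs most.

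**4. Size.** These assumptions are not in the Protocol: 162 patients in four cells of 40.5, a binary subgroup, SD 15 at each visit, a common within-patient correlation r, and complete data. At r = 0.5 the SD of change is 15 × √(2 × 0.5) = 15, which is one of the SDs in Section 8.2.

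- Planned test: SE = √[225 × (1 + 4r)/5 × 4/40.5]. At r = 0.5 this is 3.65.
- Change-based test (T5 minus T1): SE = √[2 × 225 × (1 − r) × 4/40.5]. At r = 0.5 this is 4.71.
- Rejection probability = Φ(|effect|/SE − 1.96) + Φ(−|effect|/SE − 1.96).

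The effect seen by the planned test is the five-visit mean of the subgroup difference in the group gap. The effect seen by the change-based test is T5 minus T1. At r = 0.5:

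| Subgroup difference in group gap, T1 to T5 | Mean | T5−T1 | Planned test | Change-based test |
|---|---|---|---|---|
| 6, 6, 6, 6, 6 | 6 | 0 | 38% | 5% |
| 0, 0, 0, 0, 12 | 2.4 | 12 | 10% | 72% |
| 0, 3, 6, 9, 12 | 6 | 12 | 38% | 72% |
| 0, 0, 12, 12, 12 | 7.2 | 12 | 50% | 72% |
| 0, 12, 12, 12, 12 | 9.6 | 12 | 75% | 72% |

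Simulation with 5000 trials per pattern agrees: 10.0% against 71.0% for T5 only, and 36.9% against 71.5% for the ramp. It adds two extremes. A constant 12-point gap is flagged in 90.7% against 4.7%. The profile −6, −3, 0, 3, 6, whose mean is zero but whose change differs by 12, is flagged in 5.1% against 71.4%.

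**5. Range over r.** From the same formulas:

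| r | SE planned | SE change | Constant 6, planned | T5 only 12, planned | T2–T5 12, planned | Any 12-point change, change-based |
|---|---|---|---|---|---|---|
| 0.3 | 3.13 | 5.58 | 48% | 12% | 87% | 58% |
| 0.5 | 3.65 | 4.71 | 38% | 10% | 75% | 72% |
| 0.7 | 4.11 | 3.65 | 31% | 9% | 65% | 91% |

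**The case against.** **Primary model might mean the ANCOVA.** The ANCOVA paragraph comes directly before the subgroup paragraph, and the 81 per group traces to the ANCOVA figure of 74. In the ANCOVA, group × subgroup is a proper test of effect modification at discharge given baseline. This is the strongest objection, and the point depends on it. Section 8.1, however, attaches the word primary to the mixed model and rests primary inference on it. If the ANCOVA was meant, the text should say so.

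**The term may be shorthand for the SAP to expand.** This is possible, since Section 8.1 leaves other details to the SAP. But here it names both the term and the model, and elsewhere it writes group × time in full. As worded it is a stated rule, not a gap.

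**A level-based test is not foreign to this protocol.** Section 7 words the primary endpoint as score differences at each time point. That is fair, but the two-way term also forces the subgroup modification to be equal at all five visits, so it does not serve that wording well either.

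**Stronger readings that the documents do not support.**

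- A reader might infer that real modification of change will mostly be missed. That is not general: if it is present at all of T2 to T5, the planned test does about as well as the change-based one at r = 0.5 (75% against 72%) and better at r = 0.3.
- A reader might take the 38% as type I error inflation. It is power for a level interaction that truly exists. The fault is that the test answers another question.
- A reader might infer that the secondary endpoint "Comparison of PROs by disease status and treatment line" in Section 7 also goes unanswered. That wording names neither time nor change, and disease status and line of therapy are already covariates in the model, so a level comparison is available.

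**Conclusion.** The point holds on the reading that Section 8.1 best supports, namely that the primary model is the five-visit mixed model. On that reading the cancellation is exact and needs no numerical assumption: the stated subgroup test cannot address variation in the plan's own estimand, and it mixes in the admission gap.

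The practical size does rest on assumptions (SD 15, equal subgroups, complete data, common correlation). A constant 6-point gap is flagged in roughly 31% to 48% of trials over correlations 0.7 to 0.3. The effect on detecting a true modification of change runs from severe (T5 only) to none (all of T2 to T5), according to pattern and correlation. Exact equal weighting of visits also needs a random intercept and complete or imputed visits; otherwise the average is weighted differently, with T1 still included in the random-slope case checked.

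The consequence is confined to analyses that the Protocol labels exploratory. Primary inference, sample size and data collection are untouched.

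**What to change.** In Section 8.1, Subgroup analyses, choose one of the following and state it:

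1. In the mixed model, add subgroup × time and group × time × subgroup to the group × subgroup term, and test the T5 minus T1 element of the three-way interaction, which is the same contrast as the primary parameter.
2. State that the subgroup test is the group × subgroup term in the baseline-adjusted discharge ANCOVA.

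Either is a one-line change of wording and needs no new data. Option 1 adds model terms: for three-level disease type, (3 − 1) × (5 − 1) = 8 subgroup × time and 8 three-way terms. Its interval is somewhat wider at correlation 0.5 (SE about 4.7 against 3.7 points), wider still at 0.3 (5.6 against 3.1), and narrower at 0.7 (3.7 against 4.1). Option 2 adds only the interaction terms, but it addresses discharge alone.

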- Multiple secondary endpoints and subgroup tests are planned; these will be described as exploratory. Where formal control of family-wise error is desired for predefined secondary endpoints, procedures (e.g., Holm or Benjamini-Hochberg false discovery rate) will be specified in the SAP.

Additional analyses

- **Proportion with clinically meaningful deterioration:** compute proportion of participants with ≥ 6 -point worsening from baseline to discharge and compare groups using chi-square tests and logistic regression adjusted for covariates; report risk differences and adjusted odds ratios with 95% CIs.
- **Sensitivity for clustering:** if substantial between-site heterogeneity is present, use mixed models with random site intercepts or a generalized estimating equations (GEE) approach with robust SEs clustered by site.
- **Exploratory trajectories:** use latent class growth modelling or clustering of longitudinal profiles if warranted to identify common PRO trajectory phenotypes (reported descriptively).

Reporting

- All results will be reported according to STROBE guidance for observational studies and following best practices for PRO reporting (including instrument scoring details, number of missing items, and sensitivity analyses). Statistical code and de-identified

analytic datasets will be archived as per institutional policies and will be made available on reasonable request, consistent with GDPR and ethics approvals.

8.2. Sample Size:

The primary objective was to detect a between-group difference in HM-PRO between groups based on the difference in HM-PRO total score of $\Delta = 6$ points (the established Minimal Important Difference). Assuming a two-sided $\alpha = 0.05$ and 80% power, the required sample size per group was calculated using the two-sample t-test formula:

$$n = (2(z_{(1-\alpha/2)} + z_{(1-\beta)})^2 \sigma^2) / \Delta^2$$

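### Benjamini-Hochberg is offered as a route to family-wise error control on secondary endpoints, but it controls the false discovery rate

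*Protocol*

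**What the plan says.** Protocol section 8 sets the general test level: "two-sided tests with a nominal significance level of $\alpha = 0.05$ unless otherwise stated". The multiplicity paragraph in section 8.1 then gives the default status of the secondary and subgroup analyses: "Multiple secondary endpoints and subgroup tests are planned; these will be described as exploratory". The next sentence allows an exception: "Where formal control of family-wise error is desired for predefined secondary endpoints, procedures (e.g., Holm or Benjamini-Hochberg false discovery rate"), with the procedures to be specified in the SAP.

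Section 7 lists three lines of secondary endpoints: within-group change in HM-PRO over time, "Comparison of PROs by disease status and treatment line", and adverse events with their correlation to the PRO data. Some of these lines cover several tests. The protocol does not say how many tests would form the family. HM-PRO total and domain score differences between the treatment groups are the primary endpoint, so they lie outside this sentence.

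**The concern.** The sentence sets one error rate as the goal and gives two example methods for reaching it, only one of which does so.

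- **Family-wise error** is the probability of at least one false rejection among the true nulls in the family. Holm keeps it at or below the chosen level under any dependence between the tests.
- **The false discovery rate** is the expected share of false rejections among all rejections. Benjamini-Hochberg bounds this share (under independence or suitable positive dependence). As real effects are rejected, its threshold for the remaining tests loosens, which is consistent with a false discovery target but not with a family-wise one.

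The protocol's own label for Benjamini-Hochberg, as a false discovery rate method, conflicts with the goal at the head of the sentence, and nothing elsewhere in the protocol corrects it. The exception is also the one place where a secondary result would stop being merely exploratory and be presented with formal error control. A result reported there as protected family-wise would lack that protection if Benjamini-Hochberg had been used.

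A mix of real effects and true nulls is plausible in this study. The background cites a study in which quality of life fell in all groups to a nadir around week 2, so some within-group changes over time can be expected to be real. The background gives no expectation for disease status or treatment line, so nulls may well be true there.

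**Working it through.** The plan states no figure on this point, so there is none to reproduce. The check asks how far family-wise error under Benjamini-Hochberg can depart from 5%.

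**Inputs**
- Level α = 0.05, two-sided: protocol section 8.
- Number of tests m: not given. Assumed range 3 to 10.
- Number of true nulls m0, size of the real effects, correlation between tests: not given. All assumed.

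**Rules.** Order the p-values p(1) ≤ … ≤ p(m).
- Benjamini-Hochberg: find the largest k with p(k) ≤ kα/m and reject the k smallest.
- Holm: step up from the smallest p-value, rejecting while p(k) ≤ α/(m − k + 1), and stop at the first failure.

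**Hand calculation with very large real effects and independent tests.** The m1 = m − m0 real effects are then always rejected and only the true nulls matter.

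*m = 4, m0 = 2.* Under Benjamini-Hochberg the smaller null p-value meets the threshold 3 × 0.05/4 = 0.0375, and both nulls are rejected if both are at or below 0.05.
- Benjamini-Hochberg: 1 − (1 − 0.0375)² + (0.05 − 0.0375)² = 0.0736 + 0.0002 = 0.0738.
- Holm (smaller null against 0.05/2 = 0.025): 1 − 0.975² = 0.0494.
- Simulation of 200,000 sets: 0.0736 and 0.0492.

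*m = 3, m0 = 2.* The threshold is 2 × 0.05/3 = 0.0333.
- Benjamini-Hochberg: 1 − (1 − 0.0333)² + (0.05 − 0.0333)² = 0.0656 + 0.0003 = 0.0658.
- Simulation: 0.066, with Holm 0.0493.

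*m = 10, m0 = 5.* The smallest null meets 6 × 0.05/10 = 0.03, which alone gives a lower bound.
- Benjamini-Hochberg: at least 1 − 0.97⁵ = 0.141.
- Holm: 1 − 0.99⁵ = 0.0490.
- Simulation: 0.1415 and 0.0489.

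**Effects of 3.5 standard errors, half the endpoints truly different.** Simulation, 200,000 sets per case; repeat runs differ by about 0.2 percentage points.

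| Endpoints (true nulls) | Correlation | Benjamini-Hochberg | Holm | Benjamini-Hochberg ÷ 5% |
|---|---|---|---|---|
| 4 (2) | 0 | about 7% | about 4.5% | 1.4 |
| 6 (3) | 0 | about 9% | about 4.3% | 1.8 |
| 10 (5) | 0 | about 13% | about 4.2% | 2.6 |
| 10 (5) | 0.5 | about 9.6% | about 3.5% | 1.9 |

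**Smaller effects (2.8 standard errors).** With independent tests Benjamini-Hochberg gives 6.2% for 4 endpoints (2 true nulls) and 10.8% for 10 (5 true nulls). With correlation 0.5 these fall to 5.3% and 7.8%.

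**Where Benjamini-Hochberg does hold family-wise error**
- All nulls true: 0.0491 for m = 5, 0.0507 for m = 3, i.e. 5% within simulation error.
- Exactly one true null: its largest possible threshold is mα/m = α, so the error cannot exceed 5%. Simulation for m = 5 with four very large effects gives 0.0504, which is 5% within simulation error.

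The false discovery rate under Benjamini-Hochberg was at or below 5%, within simulation error, in every case. The method does what it is designed to do, which is not what the sentence asks of it.

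**The case against.** The strongest reply is that nothing is fixed. The sentence is conditional, gives its methods as examples, names Holm first, labels Benjamini-Hochberg as a false discovery rate method, and leaves the choice to the SAP, where secondary multiplicity procedures are commonly settled. The harm arises only if the SAP opts for formal control, chooses Benjamini-Hochberg and still calls the result family-wise control. The secondary and subgroup tests are otherwise exploratory. All of this stands, and it keeps the impact small. It does not make the sentence right, because the point is not that detail is missing: the protocol itself pairs a method with a property the method lacks.

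Four stronger readings are tempting and are not supported.

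- *That the error would be two to three times 5%.* The range under the 3.5 standard error assumptions is 1.4 to 2.6. Only the case of 10 independent tests exceeds twofold, and independence is doubtful when the tests share HM-PRO data from the same patients. The 5% in section 8 is also a nominal test level, not a family-wise level set for the secondary endpoints.
- *That any one endpoint declared positive carries this error.* The figures are the chance of at least one false positive anywhere in the family.
- *That Benjamini-Hochberg holds family-wise error only if every null is true.* It also holds it with exactly one true null.
- *That the expected CAR-T versus allo-SCT difference supplies the real effects.* That difference, including domain scores, is the primary endpoint. Of the effects the background anticipates, only the within-group change over time is secondary.

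**Conclusion.** The point holds as an error of wording with a minor effect. The sentence offers Benjamini-Hochberg for formal family-wise error control, which the method does not in general provide when two or more true nulls accompany real effects. If it were chosen, the chance of at least one false positive in the family would be about 7% to 13% for 4 to 10 independent endpoints under the stated assumptions, and about 9.6% for 10 endpoints with correlation 0.5, against at most 5% with Holm. The number of endpoints, the effects and the correlation are all assumed, and smaller or more correlated families show less inflation. A reader should not infer that the study's main conclusion is at risk: the primary analysis and the sample size do not depend on this sentence.

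**What to change.** In the multiplicity paragraph of section 8.1, name only Holm, or another family-wise procedure, for predefined secondary endpoints that will be claimed under family-wise error control. If Benjamini-Hochberg is wanted for any secondary or subgroup family, say so in a separate sentence and state that only the false discovery rate is controlled there. The domain scores should not be swept into that sentence, since section 7 places them in the primary endpoint.

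The cost is one sentence of text and slightly less power on those secondary endpoints than Benjamini-Hochberg would give. No data collection, sample size or primary analysis changes.

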3.1. Overview

Prospective, multicenter, observational cohort study comparing short-term PROs measured with the HM-PRO between two exposure groups: patients undergoing allogeneic stem cell transplantation (allo-SCT) and patients receiving CAR-T cell therapy. Patients will be enrolled at hospital admission for the index inpatient procedure and followed through the inpatient stay (admission → discharge). The study is non-randomized and designed to describe trajectories of symptoms and HRQoL and to estimate the between-group difference in deterioration of HM-PRO scores (primary estimand: mean difference in change score, CAR-T vs allo-SCT).

3.2 Setting:

Two tertiary care hospitals in Rome, Italy, with active allo-SCT and CAR-T in patient programs; multicenter to improve generalizability.

3.2 Duration:

1 year enrollment, participation from hospital admission to discharge (maximum 3 months).

4. Population

One hundred and sixty-two adults (≥ 18 years) with a hematologic malignancy admitted for either (a) allo-SCT (N=81) or (b) CAR-T cell therapy (N=81).

4.1 Inclusion Criteria:

- Age ≥ 18 years
- Diagnosed with a hematologic malignancy (e.g., leukemia, lymphoma, multiple myeloma)
- Undergoing either allogeneic SCT or CAR-T therapy
- Able and willing to provide written informed consent
- Sufficient Italian proficiency to complete the HM-PRO
- Signed informed consent

4.2 Exclusion Criteria:

- Cognitive or physical impairments that preclude the ability to complete questionnaires
- Estimated life expectancy < 7 days at the time of admission

5. Assessment Schedule

Patient-reported outcomes will be collected using the HM-PRO instrument at the following time points:

- T1: Hospital admission
- T2: Day of infusion (CAR-T or stem cell infusion)
- T3: Day 3 post-infusion
- T4: Day 10 post-infusion
- T5: Day of hospital discharge

6. Collected Variables

Demographics:

- Age, Gender, Education level, occupation, civil status

Clinical Variables:

- Comorbidities, Disease type, Disease status (remission/progression), Line of treatment

Laboratory:

- Full blood counts

Treatment:

- CAR-T or allo-SCT treatment details, including conditioning regimen and product specifics

Adverse Events:

- Documented using CTCAE criteria, including:
 - Mucositis, Infections, GvHD, CRS, ICANS

Patient-Reported Outcomes:

- HM-PRO (Impact Scale, Symptoms Scale)

7. Endpoints

Primary Endpoint:

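### With only two hospitals, a GEE with robust standard errors clustered by site gives standard errors that are erratic and usually far too small

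*Protocol*

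**What the plan says.** Protocol section 3.2 (Setting) fixes the sites: "Two tertiary care hospitals in Rome, Italy". Section 4 (Population) plans "One hundred and sixty-two adults", 81 per group.

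Section 8.1 deals with site in three places:

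- The primary mixed model lists among its covariates "site (as fixed effect or as random effect in a hierarchical model". The discharge ANCOVA takes "baseline HM-PRO as covariate, plus the same prespecified covariates", so site enters there too.
- Under model diagnostics the plan will "perform sensitivity analyses using robust standard errors if necessary", without naming a clustering unit.
- Under Additional analyses, the clustering sensitivity analysis applies "if substantial between-site heterogeneity is present". It then offers two options: a mixed model with a random intercept for site, or a "generalized estimating equations (GEE) approach with robust SEs clustered by site".

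The last item mentions no small-sample correction and does not say that clustering by site leaves two clusters.

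**The concern.** A sandwich variance clustered by site measures uncertainty from how much the site-level score totals vary. It is justified when there are many sites. With two, the totals of the fitted model must be equal and opposite, so a single number carries all the information on variance. Two things follow. The standard error of any one contrast is very unstable and most often too small. The robust covariance matrix has rank 1, so a joint 4-df test of group × time over five time points cannot be formed from it.

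The analysis would be run when the sites seem to differ, to show whether the CAR-T versus allo-SCT difference survives. A standard error of about half its proper size would lend false support to that difference.

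**Working it through.** **Inputs.** From the protocol: two sites (section 3.2); 162 patients, 81 per group (section 4); two-sided 5% level and a 6-point target difference (section 8.2); SD 15 and baseline–outcome correlation 0.5, the worked example in section 8.2. Assumed: the split of patients and treatments between sites, a site SD of 0, 3 or 6 points, and the visit correlation pattern.

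**The plan's own figures.** The plan gives none for the site-clustered standard error. Its sample-size example does reproduce: 2 × (1.960 + 0.842)² × 15² × (1 − 0.5²) / 6² = 73.6, i.e. 74 per group, and 74 × 1.1 = 81.4 against the stated 81.

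**Closed form: two equal sites, same treatment mix.** Let d1 and d2 be the group contrasts in the two sites, each with variance V.

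- Overall contrast: d = (d1 + d2)/2, with true SE = √(V/2).
- Site-clustered sandwich SE = |d1 − d2| / (2√2). Since d1 − d2 has variance 2V, this equals the true SE × |Z|/√2, with Z standard normal and independent of d.
- Median ratio of estimated to true SE: 0.6745/√2 = 0.477.
- The test statistic is √2 times a Cauchy variable, so P(|t| > 1.96) = 1 − (2/π) arctan(1.96/√2) = 0.398.

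Neither the SD, the correlation nor the sample size appears in these results.

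**Small-sample variants, same setting.**

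- Uncorrected sandwich with a 1-df t reference: 1 − (2/π) arctan(12.706/√2) = 7.1%.
- Variance multiplied by G/(G − 1) = 2, with 1-df t: exactly 5%, but the median 95% half-width is 12.706 × 0.6745 × SE. The SD of change is 15 × √(2 × (1 − 0.5)) = 15, so SE = 15 × √(2/81) = 2.36 and the half-width is 20.2 points. With 146 patients (162 less 10%), SE = 2.48 and the half-width is 21.3 points.

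**Simulation, no true group effect, five visits, site as a covariate** (24 settings × 5,000 data sets; 162 or 146 patients; site splits from 50/50 to 70/30, including opposite treatment mixes). Admission-to-discharge group contrast:

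| Method | False positives | Median 95% half-width (points) |
|---|---|---|
| Clustered by site, z | 38.5–43.4% | – |
| Clustered by site, G/(G − 1), 1-df t | 4.5–5.9% | 18–22 |
| Clustered by site, additive correction | 1.9–2.5% | 5.5–6.1 |
| Clustered by patient, z | 4.9–6.0% | 4.6–4.8 |

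The uncorrected site-clustered SE had a median of 0.43–0.49 of the true SE (10th percentile 0.08–0.10, 90th 1.04–1.18). Its group × time block had rank 1 in all 120,000 data sets. The patient-clustered 4-df Wald test rejected in 5.7–6.8%.

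**Discharge ANCOVA** with baseline, six covariates and site (12 settings × 5,000): site-clustered z 39.5–41.5%; patient-level robust 4.9–5.8%; model-based 4.5–5.6%.

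**Cause.** A separate simulation with residual SD 13 gave 39–43% with two sites and 6.0% with 40 sites. The number of clusters is therefore what drives the error. In its base case the site-clustered SE was below the true SE in 84% of runs and below half of it in 52%.

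**The case against.** **Primary inference is untouched.** It rests on mixed models that already carry site. The clause is conditional, and its other option, random site intercepts, gave 4.4–6.3% false positives in simulation at 162 patients. The sponsor could follow the protocol and never run the criticised analysis. This stands, and it limits the severity.

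**The protocol names neither an uncorrected sandwich nor a normal reference.** A correction could be set in the SAP, and corrected site-clustered versions do control false positives. This stands in part: the 40% figure belongs to the ordinary sandwich with z. But the protocol itself fixes the clustering unit, whereas on other points it explicitly defers detail to the SAP. The corrections do not rescue the choice either. The 1-df version has a half-width of 18–22 points against a 6-point target. The additive version is conservative and leans on the model-based variance that the robust method is meant to avoid.

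**The SE is not always too small.** True: its 90th percentile slightly exceeds the true SE. Erratic and most often too small is the fair description.

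**Clustering on patient ignores variation of the group effect between sites.** If that effect varied with an assumed SD of 1–3 points, the true SE for an average over a population of sites would be √(2.36² + SD²/2) = 2.46–3.17. A patient-clustered z test would then reject about 6–15% (15.7% in a simulation at SD 3). This stands as a limit on scope: the replacement speaks for these two hospitals only. Two sites cannot support more, and with site-clustered z the error in the same situation was about 40%.

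**Conclusion.** The point holds, at minor severity. The protocol names a variance method that its own two-site design cannot support. Used in its ordinary form with a normal reference, it turns a nominal 5% test into one of about 40%, with a standard error typically about half the true one. The closed-form figure assumes two sites equal in size and treatment mix; across the uneven settings simulated, the error was much the same. Small-sample corrections restore error control only at the price of a nearly uninformative interval or of reliance on the model-based variance. The main mixed model, the ANCOVA with site as a covariate and the random-site-intercept option are not affected.

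**What to change.** In section 8.1, Additional analyses, replace the GEE option in the clustering item with wording such as:

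> a GEE with robust standard errors clustered on patient and site as a fixed covariate; if the sites appear to differ, a site × group term is reported as exploratory.

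The random-site options may stay, but a variance estimated from two sites is poorly determined, and the fixed site effect already allowed in the primary model is simpler.

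The cost is one clause. Data, visits and sample size do not change, and standard software suffices. There are two downsides to state openly. Inference applies to these two hospitals. The site × group term is also imprecise: on the change score its 95% half-width is 1.96 × 15 × √(4/40.5) = 9.2 points with 162 patients in balanced cells and 9.7 with 146. With opposite 70/30 treatment mixes it is 10.1 and 10.6 points. It can therefore reveal only large differences between the sites.
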